**Study Population:**

Eligibility criteria:

- Cancer survivors:
- Treatment with chemotherapy and/or radiation therapy for a primary ALL/NHL diagnosed prior to age 17 years.
- $\leq$  15 years of age at time of enrollment.
- No cytostatic drugs uptake during the study.

Exclusion criteria:

- Diagnosis of diabetes mellitus types 1 or 2 types before antitumor therapy
- Active oncological disease
- History of allogeneic hematopoietic cell transplant
- Absence of written consent for participation from the patient or legally authorized representative

Randomization: N/A
Anticipated Primary Objective Completion Date: 10/09/2018
Anticipated Study Completion Date: 10/12/2021
Analysis of objectives: Aims 1 and 2: Descriptive statistics will be used to summarize prior cancer therapy, collected from formal medical record abstraction. Epidemiological, clinical and laboratory variables, including genetic variants will be tested for their association with metabolic syndrome. McNemar's test for paired data will be used to compare the unmatched general characteristics of cases and controls. Allele frequencies will be estimated by two-side Fisher exact test, and the Chi-square test will be used to check for departures from Hardy-Weinberg equilibrium. Aim 3: The crude disease-exposure association will be determined by estimating the OR and its 95% confidence interval (CI). This will be done by univariate conditional logistic regression, to account for the matched design. The significance of the OR will be assessed by the Wald test. Exposures for which the P-value is less than 0.25 in univariate analysis will be entered into a multivariate conditional logistic regression model. Backward stepwise regression procedures will be used to develop the final multivariate model and possible interactions will be examined. The fit of the model will be assessed by the logistic regression diagnostics procedure. Haplotypes will be constructed where applicable, and pathway analysis will be used to construct multilocus genotypic groups, rather than a "one-gene-at-a-time" approach, where possible. Exploratory Aim: The multiple regression approach as described above (plan for primary Aims 1 and 2) will be implemented to assess the relationship between biomarker levels (HOMA index, triglyceridemic) and endothelial dysfunction (rigidness of arteries and positive biomarkers) with metabolic syndrome in cancer treated patients.
Data management: Data management for this study will be supervised by the Department of the study late effects of antitumor therapy, medical record data are contained in the data base of registry information of Dmitry Rogachev National Medical Research Center.
Human Subjects: The risk of harm anticipated in the proposed research is not greater than that encountered during daily activities. All assessments will be performed by the clinical practitioners and researches who has experience in their own scientific technology. Participants will not be required to complete any assessments they wish to omit. [name] will be available to answer any questions participants have regarding their treatment or medical late effects. If a participant experiences undue discomfort during any of the testing, the test will be stopped immediately.

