**Objectives:**

Specific Aim 1. Evaluate the frequency and clinical features of the metabolic syndrome in childhood cancer survivors.

Hypothesis 1A: Components of the metabolic syndrome are realized in children and adolescents at all stages of therapy of leukemia and lymphomas, can influence the development of complications and late toxic effects.

Hypothesis 1B: Initial health conditions (abnormal IBM, family history, comorbid diseases); drug's toxicity could influence to the appearance of early manifestation of metabolic syndrome.

Specific Aim 2: Evaluate the contribution of functional polymorphisms in candidate genes to metabolic syndrome outcomes among childhood cancer patients.

Hypothesis 2A: Genetic polymorphisms involved in the regulation of the insulin resistance and cancer medications during treatment contribute to the development of metabolic syndrome in childhood cancer survivors.

Specific Aim 3: Assess the extent to which genetic predictors, doses of drugs, risk factors improve the discriminatory performance of standard clinical prediction models for metabolic syndrome outcomes among childhood cancer survivors.

Hypothesis 3 A: Development of metabolic syndrome in cancer patients depends of genetic determinants and toxic effects of antitumor therapy.

Secondary Aim 1: Assess the definition of metabolic syndrome in cohort of patients of leukemia and lymphoma and survivors.

Hypothesis 1A: Episodes of triglyceridemic, insulin resistance (Hyperglycemia, HOMA $>2,7$ , Steroid Diabetes) during the treatment could be the base evidence marker of Metabolic Syndrome in patients treated by antitumor therapy.

Hypothesis 1 B: Endothelial dysfunction as a clinical component of metabolic syndrome is responsible for cardio-vascular abnormalities in cancer survivors.

**Exploratory aim 1:** Assess the association of biomarkers and genetic predictors among childhood cancer survivors with therapeutic exposures (chemotherapy and/or radiation therapy) and metabolic syndrome.

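### Hypotheses 2A and 3A concern development of metabolic syndrome, but the planned analyses use syndrome status without restricting it to new onset or ensuring adjustment for pre-therapy components

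*Protocol*

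**What the plan says.** **Hypotheses (Protocol, Objectives).** Hypothesis 2A states that genetic polymorphisms and cancer medications "contribute to the development of metabolic syndrome in childhood cancer survivors". Hypothesis 3A reads "Development of metabolic syndrome in cancer patients depends of genetic determinants and toxic effects of antitumor therapy". Both are statements about onset. Hypothesis 1B names pre-therapy status as a determinant: "Initial health conditions (abnormal IBM, family history, comorbid diseases); drug's toxicity could influence to the appearance of early manifestation of metabolic syndrome" (IBM is evidently BMI). Aim 3 asks whether "genetic predictors, doses of drugs, risk factors improve the discriminatory performance of standard clinical prediction models".

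**Eligibility (Protocol, Study Population).** The only metabolic exclusion is "Diagnosis of diabetes mellitus types 1 or 2 types before antitumor therapy".

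**Analysis (Protocol, Analysis of objectives).** For Aims 1 and 2, "Epidemiological, clinical and laboratory variables, including genetic variants will be tested for their association with metabolic syndrome", and alleles are compared by Fisher's exact test. For Aim 3, "The crude disease-exposure association will be determined by estimating the OR and its 95% confidence interval (CI"). Exposures with a univariate P-value below 0.25 then enter a multivariate conditional logistic model, which is reduced by backward stepwise selection. No variable is kept in regardless of its P-value, and the outcome is nowhere limited to cases that arose after therapy began.

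**Populations (Protocol, Sample Size and Cases).** There are two groups. One is 400 patients recruited at the start of therapy. The other is the Russkoe Pole cohort (RPC) survivors, who enter at least 6 months after completing therapy and whose history comes from a medical epicrisis with cumulative doses.

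**The concern.** A child who met the definition before the first dose and still meets it at assessment did not develop the syndrome under therapy. The analysis counts that child as a case all the same. The exclusion of prior diabetes shows that pre-existing metabolic disease was seen to matter, but it removes only one form of it.

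Two conclusions are at stake. First, pre-existing cases that are unrelated to dose add the same background to the high-dose and low-dose groups, so a real dose effect on onset looks smaller. Second, Appendix 1 selects some genes because they are associated with metabolic syndrome in adults. Such genes could act before and without chemotherapy, and an association through pre-existing disease would then be read as support for Hypothesis 2A or 3A.

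The gap is most serious for survivors. The study takes no measurement before their therapy, and the text names cumulative doses and prior cancer therapy as abstracted content but no pre-therapy metabolic component. A field that is not abstracted cannot be adjusted for later.

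**Working it through.** **No figure of the plan to reproduce.** The protocol gives no syndrome rate, no pre-therapy prevalence, no effect size and no power. The 400 and 2100 are recruitment numbers. The calculations below are illustrations on assumed rates.

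**1. The passages side by side.**

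| Element | Onset or status? |
|---|---|
| Hypotheses 2A, 3A | Onset |
| Exclusion | Removes prior diabetes only |
| Outcome in the analysis | Status, no onset restriction |
| Aim 2 allele comparison | Status, unadjusted |
| Aim 3 model | Status; initial BMI or comorbidity only if P<0.25 and retained by backward selection |

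**2. Dose effect.** Assume total prevalence T = 15%, half of the patients on high dose, a true odds ratio of 2.0 for new onset, and pre-existing syndrome that is unrelated to dose and persists. Let s be the share of cases that pre-date therapy.

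- Pre-existing risk: p = s × T.
- New-onset risks r0 (low dose) and r1 (high dose) solve odds(r1) = 2 × odds(r0) and p + (1 − p)(r0 + r1)/2 = T.
- Observed risk in each dose group: P = p + (1 − p) × r.
- Observed odds ratio: odds(P1)/odds(P0).

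| s | p | r0 | r1 | P0 | P1 | Observed OR |
|---|---|---|---|---|---|---|
| 5% | 0.0075 | 0.102 | 0.185 | 0.109 | 0.191 | 1.94 |
| 10% | 0.015 | 0.097 | 0.177 | 0.111 | 0.189 | 1.88 |
| 20% | 0.030 | 0.087 | 0.160 | 0.115 | 0.185 | 1.76 |
| 33% | 0.050 | 0.074 | 0.137 | 0.120 | 0.180 | 1.61 |
| 50% | 0.075 | 0.056 | 0.106 | 0.127 | 0.173 | 1.44 |

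The odds ratios use unrounded risks. With T = 10% or 20%, they change by at most 0.02. The bias is always towards 1.

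**3. Gene effect.** Assume a gene with odds ratio 2 on pre-existing syndrome and no effect on new onset, which is 10% in everyone free of the syndrome at the start. Let p be the pre-therapy prevalence in non-carriers and q that in carriers.

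- odds(q) = 2 × odds(p).
- Status at assessment: p + (1 − p) × 0.10 in non-carriers, q + (1 − q) × 0.10 in carriers.

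| p | q | Non-carriers | Carriers | Apparent OR |
|---|---|---|---|---|
| 2% | 3.9% | 11.8% | 13.5% | 1.17 |
| 5% | 9.5% | 14.5% | 18.6% | 1.34 |
| 10% | 18.2% | 19.0% | 26.4% | 1.53 |

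The true odds ratio for onset is 1.0 in each row, so the whole apparent effect comes from disease that was there before therapy.

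**The case against.** **Adjustment is possible under the plan.** Hypothesis 1B names initial BMI, family history and comorbidity, Aim 3 sets risk factors beside genes and doses, and the multivariate model can hold them. A strong initial BMI effect would probably pass P<0.25. This stands against any claim that nothing adjusts. It does not secure the adjustment. Nothing is forced in, and initial hypertension or dyslipidaemia is covered at most by comorbid diseases. The Exploratory Aim refers back to multiple regression for Aims 1 and 2, but the only model described is under Aim 3. Nor does a covariate turn prevalent disease into new onset.

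**A component is not the syndrome.** A child with obesity alone before therapy is not a prior case. This stands. The share of cases that fully pre-date therapy is unknown, and at 5% or 10% the dilution is slight (1.94 or 1.88).

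**Prediction is a legitimate aim.** Aim 3 is worded as discriminatory performance. For prediction, a persisting baseline condition is signal and not bias. This stands for prediction, and it is also a reason not to force baseline status into every model. It does not answer Hypothesis 3A, which sits under the same aim and is about what development depends on.

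**The detail could be left to an SAP.** The choice of covariates could. The hypotheses, the exclusion, the outcome wording and the selection rule all stand in the protocol, and they do not match.

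**Stronger readings that the documents do not support.** A reader might infer that pre-existing disease will appear as a treatment effect. All patients are treated, and pre-existing disease unrelated to dose dilutes the dose odds ratio and cannot create one. A reader might also infer that the Aim 1 frequency is inflated as a therapy effect, but Aim 1 only describes frequency and clinical features.

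**Conclusion.** The point holds as a mismatch between hypotheses about development and an analysis of status. Followed as written, the plan mixes pre-existing with new-onset syndrome and does not ensure adjustment for pre-therapy components.

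The size cannot be fixed from the document. If the true dose odds ratio is 2.0 and prevalence is 15%, the observed value is 1.94 to 1.44 as the pre-existing share runs from 5% to 50%. A gene with odds ratio 2 on pre-existing disease alone would show 1.17 to 1.53 for pre-therapy prevalence of 2% to 10% with 10% new onset. Both ranges assume that pre-existing syndrome persists, and the first also that it is unrelated to dose. If pre-therapy syndrome is rare, the effect is small.

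The change should be made. It is cheap, and without it the results cannot support the word development.

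**What to change.** - **The 400 patients recruited at the start of therapy:** record each component before therapy. Test Hypotheses 2A and 3A on new onset, or on the follow-up value adjusted for the baseline value.
- **RPC survivors:** abstract pre-treatment BMI and comorbidity from the epicrisis, with blood pressure and lipids where recorded. Keep these in the dose models whatever the P<0.25 and backward-selection rules give. Report gene models with and without them, because a gene may act through baseline status and adjustment would then remove part of its effect.
- **Wording:** describe survivor results as prevalence, and reserve development for patients with a known baseline.

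**Cost:** some abstraction work and changed model text. Children with a pre-existing component leave the new-onset analysis of that component. The protocol does not say that the epicrisis holds pre-treatment blood pressure or lipids, so survivor adjustment may stay incomplete. That is a further reason to rest the onset hypotheses on the 400.

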**Evaluation:**

Eligible persons who consent to participate in this trial will be asked to do the following:

- Vital sign measurement including resting heart rate, blood pressure, height, and weight.
- A total of 12 mL of blood will be collected in 3 test tubes. Biomarker analysis will be completed by Laboratory of Dmitry Rogachev National Medical Research Center.
- A Total of 4 mL of blood in 1 test tube will be used for genotyping for the presence of polymorphic variants in genes involved in biotransformation of xenobiotics, insulin resistance and carbohydrate metabolism in the biomolecular laboratory of Dmitry Rogachev National Medical Research Center.
- An echocardiogram and ultrasound will be performed to assess cardiac function.
- CAVI and ABI pulse wave velocity will be non-invasively measured by using the SphygmoCor VaSera VS-1500N. Arterial pressure waveforms will be recorded with a strain gauge pressure sensor placed lightly over the radial artery before and after “6-minutes physical activity”.

**Study Design:** Longitudinal

**Sample Size:** Aims of this study will be accomplished using a longitudinal assessment of 400 patients with ALL/NHL from Dmitry Rogachev National Medical Research Center and other Regional Clinics will be recruiting to the cohort at the start of the therapy MB-ALL/ BFM-NHL. Potentially 2100 survivors ALL/NHL will be treating in “Russkoe Pole” 2018-2021.

**Cases:** Participants for this study will be patients of “Russkoe Pole” cohort (RPC), a longitudinal study designed to evaluate health among children and adolescents survivors of childhood leukemia and lymphoma as they age. Participants in RPC undergo risk-based medical screening according to the Standards of Medical Insurance for rehabilitation of Cancer treated patients. Cases will be stratified by survival time (1-4, 5-9, and  $\geq$  10years).

To be eligible for RPC, cancer survivors must have been treated in Russian children oncology clinics by MB-ALL/ BFM-NHL and be 15 years of age or younger, and at least 6 months from the completion of the therapy. All the patients will have exhaustively full epicrisis of medical history with cumulative doses of medications. Because RPC is a retrospective cohort study with ongoing recruitment (additional survivors become eligible over time).

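### The only genetic test named under Aims 1 and 2 is an unadjusted Fisher test on alleles, in a multi-clinic cohort where no model carries a region term

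*Protocol*

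**What the plan says.** Aim 2 in the protocol's Objectives is to "Evaluate the contribution of functional polymorphisms in candidate genes to metabolic syndrome outcomes among childhood cancer patients". The Analysis of objectives paragraph, under Aims 1 and 2, first makes a general statement: "Epidemiological, clinical and laboratory variables, including genetic variants will be tested for their association with metabolic syndrome". It names no method for this. The one procedure it then names for the genetic data is "Allele frequencies will be estimated by two-side Fisher exact test", followed by a chi-square check of Hardy-Weinberg equilibrium.

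Regression appears only under Aim 3. Univariate conditional logistic regression is used there because the design is said to be matched, and then "Exposures for which the P-value is less than 0.25 in univariate analysis will be entered into a multivariate conditional logistic regression model". The matching factors are not given. The Exploratory Aim refers back to a multiple regression and labels it the plan for primary Aims 1 and 2, although none is described under those aims.

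On recruitment, the Sample Size paragraph describes "400 patients with ALL/NHL from Dmitry Rogachev National Medical Research Center and other Regional Clinics" and adds "Potentially 2100 survivors ALL/NHL will be treating in “Russkoe Pole” 2018-2021". Under Cases, "cancer survivors must have been treated in Russian children oncology clinics by MB-ALL/ BFM-NHL". No analysis names region, clinic or ancestry.

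**The concern.** There are three faults in what the protocol fixes.

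- **The test is misdescribed.** A Fisher exact test returns a p-value for a difference in proportions. It does not estimate an allele frequency.
- **The test cannot use the design.** It works on one pooled 2x2 table of alleles. If cases and controls are matched, as Aim 3 says, the test ignores the matching. If they are not, nothing in it accounts for where a child was treated.
- **The text is inconsistent about which analysis answers Aim 2.** The Aims 1 and 2 wording gives Fisher, while the Exploratory Aim implies a regression.

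What is at stake is confounding by population structure. When regions differ in both allele frequency and background risk, the higher-risk region is over-represented among cases and brings its allele frequency with it. An allele with no effect then looks associated with the syndrome. Appendix 1 lists 23 SNPs, so this could recur across many comparisons.

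**Working it through.** The protocol gives no allele frequency, syndrome risk, significance level or power for this comparison, so there is no figure to reproduce. N=400 and N=2100 come from the Sample Size paragraph. Everything else is assumed: two equal-sized regions, no true gene effect, unmatched sampling, two-sided 5% level.

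**Lead illustration.** Allele frequency p = 0.2 and 0.4; risk r = 0.10 and 0.20.

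- Allele frequency in cases = Σ(r·p)/Σr = (0.10×0.2 + 0.20×0.4)/0.30 = 0.333.
- Allele frequency in controls = Σ((1−r)·p)/Σ(1−r) = (0.90×0.2 + 0.80×0.4)/1.70 = 0.294.
- Spurious OR = (0.333/0.667)/(0.294/0.706) = 1.20.
- At N=400 the average risk of 15% gives 60 cases and 340 controls, so 120 and 680 alleles. The pooled frequency is 0.30. SE = √[0.30×0.70×(1/120 + 1/680)] = 0.0454, and z = 0.0392/0.0454 = 0.86.
- False-positive rate = P(Z > 1.96 − 0.86) + P(Z < −1.96 − 0.86) ≈ 14%.
- At N=2100, z = 0.864×√(2100/400) = 1.98, giving about 51%. Simulation of the Fisher test itself gives about 14% and 48% to 49%.

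**Milder illustration.** p = 0.2 and 0.3, same risks.

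- Cases: 0.08/0.30 = 0.267. Controls: 0.42/1.70 = 0.247. OR = 1.11.
- At N=400, SE = √[0.25×0.75×(1/120 + 1/680)] = 0.0429 and z = 0.46, giving about 7%. At N=2100, z = 1.05, giving about 18%.

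**Range over other assumed values** (simulation, 2000 runs per scenario, pooled Fisher test):

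| Allele frequency | Risk | Spurious OR | N=400 | N=2100 |
|---|---|---|---|---|
| 0.25 vs 0.35 | 15% vs 25% | 1.08 | 6.3% | 14.1% |
| 0.25 vs 0.35 | 10% vs 30% | 1.16 | 11.1% | 43.4% |
| 0.20 vs 0.40 | 15% vs 25% | 1.16 | 11.7% | 40.9% |
| 0.20 vs 0.40 | 10% vs 30% | 1.33 | 33.2% | 92.7% |
| Only one of the two differs | | 1.00 | 4% to 5% | 4% to 5% |

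**What removes it.** A region-stratified Cochran-Mantel-Haenszel test held 4.4% to 5.9% in all 18 unmatched scenarios. If controls are matched 1:1 to cases on region, both groups have the same regional mix, so the OR returns to 1.00. In the most extreme row the pooled Fisher test then gave about 4%.

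The spurious OR is the same at both sample sizes. Only the chance of declaring it significant grows with N.

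**The case against.** The strongest reply is that Fisher may not be the whole Aim 2 analysis. The general association sentence names no method, Aim 3 models genetic predictors alongside drug doses, and the Exploratory Aim speaks of a regression for Aims 1 and 2. This stands in part: the protocol does not clearly commit to Fisher alone. But the regression is not described under Aim 2, and the Aim 3 model names no region term, so neither removes the problem.

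Second, the design is called matched, and matching on region would remove the bias. That is correct. However, the matching factors are not stated, so it cannot be relied on.

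Third, the size rests wholly on assumptions. The protocol gives no regional figures, both quantities must differ, the milder case adds only about two percentage points at N=400, and 2100 is only a potential number. All of this stands and limits the claim. An unseen statistical analysis plan may also add adjustment.

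Stronger readings are tempting but not supported:

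- **That therapy confounds the gene effect.** Inherited genotype precedes treatment, so therapy confounds only where it tracks region or ancestry, and nothing in the protocol shows that it does. Cumulative doses are collected, and drug doses fall within Aim 3.
- **That counting two alleles per child seriously inflates error.** For an inbreeding coefficient of 0.01 to 0.10 the rate is only 5.1% to 6.2%, and a Hardy-Weinberg check is planned.
- **That region is already an abstracted covariate.** The protocol mentions treatment history and cumulative doses, not region.

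**Conclusion.** The point holds in a conditional form. As written, the only genetic test named under Aims 1 and 2 is ill-described, ignores any matching and cannot account for clinic or region. The text also conflicts over whether a regression belongs to those aims. These faults are in the wording and need no assumption.

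The numerical consequence does need assumptions: both allele frequency and risk differ by region, and controls are not matched on region. Then the false-positive rate ranges from about 6% to 33% at N=400 and from about 14% to 93% at N=2100 over the values tried, with 14% and about 50% in the lead illustration. If only one quantity differs, or matching is on region, there is no inflation. A reader might infer that the study's gene findings will be biased; the documents do not show that, because they give no regional data. The point is worth correcting because the test is stated and a better-suited one costs little.

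**What to change.** - Make the Aim 2 analysis a per-child logistic regression of metabolic syndrome on genotype coded 0/1/2, adjusted for or stratified by treating clinic or region, age and sex. If matching is used, make it conditional on the matched sets.
- State the matching factors, or drop the reference to matching.
- Report allele frequencies descriptively with confidence intervals, and remove the claim that Fisher's test estimates them.
- Correct the Exploratory Aim cross-reference so that it points to the regression where it is actually described.
- Let therapy enter as a covariate or gene-drug term for Hypothesis 2A, not as a presumed confounder.

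The cost is a wording change, a few degrees of freedom for clinic or region, and the work of taking treating clinic from the medical record, since it is not named as a collected variable. Clinic is an imperfect proxy for ancestry, so some residual structure may remain.

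### The protocol prescribes McNemar's test and conditional logistic regression for a matched design, but describes a cohort and defines no controls, pairs, matching factors or ratio

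*Protocol*

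**What the plan says.** The design text stands in the Protocol under Evaluation. The study design is given as longitudinal. Under Sample Size: "Aims of this study will be accomplished using a longitudinal assessment of 400 patients with ALL/NHL", who "will be recruiting to the cohort at the start of the therapy MB-ALL/ BFM-NHL"; a pool of potentially 2100 survivors is also named. The paragraph labelled Cases covers all participants from the survivor cohort (RPC), and "Cases will be stratified by survival time" in three bands (1-4, 5-9, and 10 or more years). The eligibility criteria under Study Population describe one group, treated ALL/NHL survivors.

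The analysis text follows under Study Population, Analysis of objectives:

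- Aims 1 and 2: "Epidemiological, clinical and laboratory variables, including genetic variants will be tested for their association with metabolic syndrome". Then: "McNemar's test for paired data will be used to compare the unmatched general characteristics of cases and controls".
- Aim 3, crude odds ratios: "This will be done by univariate conditional logistic regression, to account for the matched design".
- Aim 3, final model: "Exposures for which the P-value is less than 0.25 in univariate analysis will be entered into a multivariate conditional logistic regression model".
- Exploratory aim: "The multiple regression approach as described above (plan for primary Aims 1 and 2) will be implemented".

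**The concern.** McNemar's test and conditional logistic regression both need sets fixed by the design: a case with its own control or controls, or strata that contain both affected and unaffected children. The analysis text asserts such a design, but the design, sample-size and eligibility text does not contain one. The word case also shifts meaning. Under Evaluation it covers every RPC participant. In the analysis text it seems to mean a child with metabolic syndrome, since that is the outcome tested for association.

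At stake are the comparison of general characteristics, the central Aim 3 model and probably the exploratory regression. As written, the analyst would have to choose the sets, possibly after seeing the data, and the estimate and its precision depend on that choice.

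**Working it through.** **Text check.** The protocol gives no figure on this point to reproduce; the 400 has no alpha, power or effect size behind it. The elements a matched analysis needs, set against the text:

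| Needed | Found |
|---|---|
| Control group, with source and eligibility | None; controls are named only in the McNemar sentence |
| Definition of a pair or set | None |
| Matching factors | None; survival time is a stratification of cases and is not called matching |
| Ratio | None |

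**With no sets.** If each child is its own set, the conditional likelihood is empty. In one simulated cohort of 400, the software dropped all 400 observations and gave no estimate.

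**Readings under which sets could exist.** The protocol states none of them.

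(a) *Survival-time strata as sets.* Simulated with exposure 40%, OR 2 and prevalence of about 10, 20 and 30%, in 200 cohorts each. The log OR differed from stratum-adjusted unconditional regression by at most 0.002 (N = 2100) or 0.004 (N = 1000), and the standard errors were practically equal (for example 0.1481 against 0.1482). The odds ratios are sound. What is missing is the stratum effects, which matter for discrimination between strata. As an illustration, take three equal strata, a clinical exposure (40%, OR 2) and a variant (40% carriers, OR 1.5). With assumed stratum prevalences of 10/20/30%, adding the variant moves the AUC from 0.581 to 0.604 without stratum effects (gain 0.023) and from 0.670 to 0.681 with them (gain 0.011). With equal prevalences there is no difference. Discrimination within strata is not affected.

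(b) *A matched comparison of children with and without metabolic syndrome, nested in the cohort.* Assumptions: prevalence p of 10, 20 or 30%; exposure p0 = 0.30 in unaffected children; OR 2; matching unrelated to exposure. Write q for 1 minus the exposure proportion.

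- p1 = 2 × 0.30 / (0.70 + 2 × 0.30) = 0.4615
- Whole-cohort variance of the log OR, per child: 1/(p·p1·q1) + 1/((1−p)·p0·q0), with p1·q1 = 0.2485 and p0·q0 = 0.21
- 1:1 conditional variance: 1/(p·I), with I = (p1·q0 + p0·q1) × OR/(1+OR)² = 0.4846 × 2/9 = 0.1077
- Information lost = 1 − whole-cohort variance / conditional variance

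| p | Whole cohort | 1:1 pairs | Ratio | Lost |
|---|---|---|---|---|
| 10% | 45.53 | 92.86 | 2.040 | 51% |
| 20% | 26.07 | 46.43 | 1.781 | 44% |
| 30% | 20.22 | 30.95 | 1.531 | 35% |

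Near the null the ratio is (1 + 1/m)(1 − p) for m controls per case, so 1:1 loses 44, 38 and 29%. At OR 2, two controls per case lose 31, 21 and 8%; four lose 14% at p = 10% and 1% at p = 20%. The result also depends on the pairing itself: in one simulated cohort of 400 with 94 affected children and a full-cohort OR of 2.71, the central 95% of 2000 arbitrary 1:1 pairings gave ORs from about 1.84 to 4.75.

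(c) *Survivors against an external group.* No such group is defined or made eligible, so nothing can be computed.

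**Exploratory aim.** Its sentence attributes the regression to the plan for Aims 1 and 2, but none is described there. The only regression above it is the conditional one under Aim 3.

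**The case against.** The strongest reply is that the protocol does assert a matched design, that a longitudinal cohort can hold a nested case-control comparison, and that matching factors and ratio could be left to a statistical analysis plan. This stands as far as it goes. A reader might infer that McNemar's test could never be run here, or that the study has no matched component at all. The text does not support that: under a nested or external 1:1 comparison, pairs would exist. What does not stand is that a later plan could simply add the detail. The protocol relies on a control group that its design and eligibility text never mentions, and that conflict lies in the protocol itself.

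A reader might also take McNemar's test on unmatched characteristics as a contradiction in terms. It need not be one, because the phrase can mean characteristics not used for matching.

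Next, the consequences may be small: sound odds ratios under reading (a), negligible loss under (b) with several controls per case, and no bias shown under any reading. That is correct. The figures rest wholly on assumed inputs and on ratios the protocol does not propose, so they illustrate a possible consequence and do not measure an error.

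Finally, the link to the exploratory regression is an inference, since the sentence itself points to Aims 1 and 2. It is probable but not certain.

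**Conclusion.** The point holds as an internal conflict that must be resolved before analysis: McNemar's test and the Aim 3 model presuppose matched sets that the protocol does not define, and neither can be run as written without an undocumented choice. This conclusion rests on the text alone and needs no assumption.

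Its size depends on the choice made. Strata as sets leave the odds ratios sound but omit stratum effects from Aim 3's discrimination. Pairs formed 1:1 afterwards discard unmatched children and lose about 35 to 51% of the information at OR 2, under the assumed prevalence and exposure; more controls per case lose much less.

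A reader might infer that the Aim 3 odds ratios would be biased, or that every analysis fails. The documents support neither. The descriptive summaries and the Hardy-Weinberg test need no matching. Fisher's test of allele frequencies needs none either, but it does need two defined groups, and these would be missing if an external control group is meant.

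**What to change.** For children with versus without metabolic syndrome within the cohort, delete the reference to a matched design, the word conditional and McNemar's test. Use unpaired tests (chi-square or Fisher, t or Wilcoxon) and unconditional logistic regression on all survivors, adjusted for survival-time stratum, and name the same model for the exploratory aim. Where a child contributes repeated outcomes, account for clustering on the child, for example by GEE or a mixed logistic model. The cost is wording only, with no new patients or data.

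If a matched comparison is truly intended, nested or external, reconcile the Evaluation and Study Population text by defining the controls, the matching factors and the ratio. An external group would also have to be recruited, and defined for the Fisher comparison.

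Separately, recruitment of the 400 patients at the start of therapy must be reconciled with the eligibility text, which bars cytostatic drugs during the study and excludes active cancer, before it is decided how those patients enter the model.
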